Risk-reduction bilateral salpingo-oophorectomy (RRSO) after completion of childbearing has become the standard-of-care for prevention of gynecologic and breast cancer in BRCA1 or BRCA2 gene mutation carriers. Although surgery reduces the risk of death due to cancer by over 75%, knowledge regarding the impact of this procedure and subsequent hypogonadism on brain structure, function and neurotransmitter systems is limited. Menopause before the age of 40 is associated with significant cognitive decline in the years that follow and an almost 2-fold increased risk of dementia if a woman does not supplement with estradiol (E2). However, E2 is not an option for many post-RRSO women due to enhanced risk of cancer. Systematic assessment of a large group of women who underwent RRSO suggests subjective deficits in executive functions (EF), with severity inversely correlated with age at RRSO. As the prefrontal cortex is impacted by loss of E2 and is critical for working memory and other EFs, we propose to examine the biological and behavioral impact of the psychostimulant lisdexamfetamine (LDX) in 100 women between the ages of 35 and 58 with post-RRSO EF complaints. LDX is FDA approved for the treatment of attention deficit hyperactivity disorder which is characterized by many of the symptoms reported by some peri- and postmenopausal women. Participants in this study will undergo multi-modal imaging (functional magnetic resonance spectroscopy, fMRI; and proton magnetic resonance spectroscopy, ¹H-MRS) using the ultrahigh magnetic field strength of 7 Tesla pre- and post- a 6-week course of the psychostimulant lisdexamfetamine (LDX; Vyvanse®) or placebo followed by an approximate 2-week washout before crossing over to the other condition. Our overarching aim is to determine the impact of LDX treatment on brain function (neural activation and chemistry) as it relates to subjective and objective measures of EFs such as 1) organization and activation for work, 2) attention and concentration, 3) alertness, effort, processing speed, 4) managing affective interference, and 5) working memory, accessing recall. LDX has already demonstrated the potential to improve new-onset EF difficulties among women who underwent a natural menopause and has provided important information regarding a potential mechanism of therapeutic action, specifically LDX-induced changes in dorsolateral prefrontal cortex (dlPFC) glutamate (GLUT) levels.

Background

It is becoming standard of care to recommend that premenopausal women who carry BRCA 1/2 gene mutation(s) undergo risk-reducing bilateral salpingo-oophorectomy (RRSO) upon completion of child bearing. Though RRSO before the age of 40 is associated with an 80% reduction risk of ovarian, fallopian tube, and peritoneal cancer, premature menopause is associated with significant cognitive decline in the short-term and an almost 2-fold increase risk for dementia in the long-term if subsequent intervention is not utilized (Finch et al., 2014; Domchek et al., 2010; Ryan et al., 2014). Preliminary data suggest varying degrees of executive function difficulties occur in 30% to 50% of women post-RRSO. Cognitive domains particularly affected by early menopause include verbal memory (Sherwin & Henry, 2008), verbal fluency and processing speed (Ryan et al., 2014), and executive functions such as attention, organization, and working memory in some women ([name], et al., 2011).

Treatment of executive function difficulties with estradiol therapy (ET) after surgery is relatively contraindicated for some women who undergo RRSO. Overall rates of ET use after RRSO are between 25% and 47% (Madalinska et al., 2006). Moreover, longer periods of time without ET after RRSO may diminish the potential positive impact of ET (Maki, 2013; Rocca et al., 2011,

2012). Women who experience cognitive difficulties after RRSO may put off use of ET due to fear of breast cancer, diminishing the potential benefits of ET should they reconsider treatment to mitigate cognitive changes. However, ET is only partially protective even if utilized within the first month of surgical menopause as certain domains of cognitive function such as spatial memory may not be amenable to ET (Ryan et al., 2014). Hence women and their oncologists must conduct a cost benefit analysis between a potential life-saving procedure and preservation of quality of life. Given that premature menopause has adverse effects on cognitive function at a time in a woman's life when she is experiencing the greatest demands professionally and personally, it is imperative to seek alternative interventions.

Our group has explored the use of other pharmacologic strategies to target executive systems with the goal of improving symptoms of executive function difficulties. We have conducted two RCTs with medication marketed for the treatment of attention deficit hyperactivity disorder (ADHD), one with the non-psycho stimulant atomoxetine (ATX, Straterra®) and two with the pro-drug and psycho stimulant lisdexamfetamine (LDX, Vyvanse®) in the treatment of executive function difficulties in perimenopausal and menopausal women. Women who participated in the ATX study reported a significant improvement in concentration/attention and working memory domains of the Brown Attention Deficit Disorder Scale (BADDs) ([name] et al., 2011). Participants in both LDX studies were also invited to undergo the brain-imaging paradigm that is described for the current study.

[figure not shown]
Figure 1 shows the main outcome of the published results, specifically that LDX was more effective than placebo at decreasing scores in 4 of the 5 BADDs subscales ([name] et al., 2015). Findings from the imaging sub-study indicated that baseline glutamate (Glut) levels were correlated with baseline severity of total BADDs scores, meaning that individuals presenting at baseline with higher severity of executive function difficulties also had higher Glut levels within the left dorsolateral prefrontal cortex (DLPFC) at baseline. Additionally, the decline in BADDs subscale 1 (Organization and Activation) scores during LDX vs. placebo treatment was negatively associated with increase in left DLPFC blood oxygen dependent (BOLD) signal during a working memory task (N-Back). That is, the increase in left DLPFC BOLD signal to active drug compared to placebo was greater in people who had greater improvement in BADDs score on LDX vs. placebo. These findings provide important evidence of co-occurring behavioral and brain changes with LDX treatment. Applying this paradigm in a larger sample of women from whom we will also acquire neurocognitive data to assess objective changes in function will provide important information regarding the mechanism of therapeutic action of LDX in this unique population.

1 Study Objectives

1.1 Overall Objectives

The overarching aim of this study is to determine the impact of LDX treatment on brain function (neural activation and chemistry) as it relates to subjective and objective measures of executive functioning.

1.2 Primary Outcome Variable(s)

LDX effects on subjective report of executive function difficulties. Brown Attention Deficit Disorder Scale (BADDs) is a clinically administered 40-item questionnaire that assess the frequency and severity of five clusters of symptoms: 1) organization and activating for work, 2) sustaining attention, 3) sustaining alertness, 4) managing affective interference, and 5) using working memory and accessing recall. The total BADDs score will serve as the primary outcome variable, while sub-scale scores will be examined to more fully determine the impact of LDX treatment on various domains of executive function and to determine whether any sub-categories of executive difficulty are more responsive to LDX treatment in this particular population.

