4.1 Statistical Analysis

Summaries of each outcome (BADDs scores, performance on the cognitive tasks, Glut, and BOLD signal) under each treatment condition (baseline, LDX, and placebo) will be examined using histograms, boxplots, and normal probability plots. Transformations of the outcomes will be considered as necessary to meet modeling assumptions. General linear regression (mixed models) will be employed to estimate the association between each outcome, treatment condition and cross-over sequence while accounting for the nonzero correlation among the repeated observations within individuals.

Aim 1: Total BADDs score at each time point will be examined for an interaction effect between time (pre vs. post) and treatment (LDX vs. placebo) to assess whether within-subject total BADDs score is significantly reduced post LDX treatment rather than post placebo. Baseline BADDs scores will be dichotomized at the median score and considered as a covariate in the mixed effects models. Additional interaction terms for baseline group by time (pre vs. post) and baseline group by treatment (LDX vs. placebo) will be added to the model to test whether treatment effects differentially affect those with higher baseline scores.

Aim 2: Similar models will evaluate BADDs subscores, cognitive task performance, and L-DLPFC Glut levels. Similar mixed models will assess associations between change in specific BADDs domains with identified deficits in executive function and change in DLPFC Glut levels.

Aim 3: We will quantify associations between baseline percentage BOLD signal change during performance of the n-back (3-back) and L-DLPFC Glut.

Current methods for fMRI analyses are as follows: Functional scans will be realigned, normalized, time-corrected, and spatially smoothed by an 8 mm FWHW Gaussian kernel. The time series will be high-pass filtered to correct for drift across the scan. For blocked designed experiments (3-back), regressors will represent trial conditions; for the event-related design

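### Section 1.2 asks whether some BADDs domains respond more to LDX than others, but the Aim 2 models contain no comparison between domains and so do not test it

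*Combined protocol and SAP*

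**What the plan says.** Section 1.2 fixes the primary variable: "The total BADDs score will serve as the primary outcome variable". It then gives the five subscales two supporting uses. One is to describe the effect of LDX in each domain. The other is "to determine whether any sub-categories of executive difficulty are more responsive to LDX treatment in this particular population".

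Section 4.1 describes mixed models "to estimate the association between each outcome, treatment condition and cross-over sequence". Aim 1 tests a time-by-treatment interaction on the total score. The only effect modifier it adds is baseline severity, split at the median. Aim 2 covers the subscales in one sentence: "Similar models will evaluate BADDs subscores, cognitive task performance, and L-DLPFC Glut levels". Its other sentence relates change in certain domains to change in glutamate and does not compare domains with each other.

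Section 4.2 sizes the trial at 88 women for 0.3 SD of the difference in within-subject change between LDX and placebo. It equates that effect with a 19% difference on the organization/activation subscale and 15% on attention/concentration.

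The Background summarises an earlier LDX trial by the finding that "LDX was more effective than placebo at decreasing scores in 4 of the 5 BADDs subscales".

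**The concern.** Whether one domain is more responsive than another is a question about the difference between two LDX effects. A model of a single subscore estimates LDX against placebo within that domain. A significant result in one domain beside a non-significant result in another does not show that the two effects differ. Section 4.1 names no domain factor, no contrast between domains, no common scale for the subscales and no decision rule.

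At stake is a secondary claim: that LDX acts selectively on some executive functions after RRSO. Without a planned contrast, such a claim could come from chance variation among five tests. It could also come from the choice of scale, because on the plan's own figures one standardised effect looks like 19% in one domain and 15% in another.

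**Working it through.** **1. Reproduce the plan's sample size.** Inputs from section 4.2: alpha 5%, power 80%, effect 0.3 SD of the within-subject difference. The plan does not say whether the test is one- or two-sided. The two-sided paired normal formula gives n = ((1.960 + 0.842)/0.3)² = 87.2, rounded up to 88, as stated. (One-sided would give 69.) Power at n = 88 is 80.4% by the normal formula and 79.5% by the t test. Recruiting 100 with the 10% drop-out in section 3.1 leaves 100 × 0.90 = 90.

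**2. What separate models leave out.** In units of the difference SD, the LDX effect in each domain has variance 1/n. The gap between two domains has variance 2(1 − ρ)/n, where ρ is the correlation between the two domains' LDX–placebo differences. At n = 88 the standard error of the gap is √(1.4/88) = 0.126 at ρ = 0.3 and √(0.2/88) = 0.048 at ρ = 0.9. Separate models do not supply ρ. Treating the two estimates as independent gives √(2/88) = 0.151, which is too large by a factor of 1/√(1 − ρ), or 1.2 to 3.2 over that range.

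**3. How often five separate tests would split when all domains respond equally.** The documents give no ρ, so 0.3 to 0.9 is assumed. If the tests were independent with 80% power each, P(some but not all significant) = 1 − 0.8⁵ − 0.2⁵ = 67%. With correlation, this was simulated: 20,000 trials per setting, five multivariate normal LDX–placebo differences per woman with the same true effect, and five two-sided 5% t tests. Percentage of trials with a mixed pattern at n = 88:

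| True effect in every domain | ρ = 0.3 | 0.5 | 0.7 | 0.8 | 0.9 |
|---|---|---|---|---|---|
| 0.2 SD | 79.3 | 66.8 | 52.0 | 41.7 | 29.8 |
| 0.3 SD | 56.3 | 47.7 | 36.6 | 29.8 | 21.2 |
| 0.4 SD | 16.6 | 13.6 | 10.5 | 8.8 | 6.2 |
| 0.5 SD | 1.7 | 1.5 | 1.3 | 1.0 | 0.7 |

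At 0.3 SD, the rate is 46% (ρ = 0.5) and 35% (ρ = 0.7) with 90 women, and 40% and 31% with 100.

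**4. The joint test on the same data.** A Hotelling test on the four contrasts between domains called equal responses different in 4.8 to 5.3% of trials at n = 88. Its power at n = 88:

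| True pattern | ρ = 0.3 | 0.5 | 0.7 | 0.8 |
|---|---|---|---|---|
| Four domains 0.3 SD, one none | 64% | 80% | 96% | over 99% |
| Four domains 0.3 SD, one 0.5 SD | 30% | 42% | 66% | 84% |

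**5. Why the scale must be fixed in advance.** As an illustration, assume equal variances and take the difference of two end-of-trial scores with within-woman correlation r. An effect of 0.3 difference-SD then equals 0.3 × √(2(1 − r)) in baseline SD: 0.35, 0.30 and 0.23 for r = 0.3, 0.5 and 0.7. Domains that respond equally on one scale can therefore differ on the other.

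**The case against.** A reader might infer that the plan will call domains responsive according to which p-values fall below 5%. It does not say so. The count of subscales in the Background summarises another trial and is not a rule for this one. What stands is that section 4.1 offers no other rule, so the rates in step 3 show what would follow if that practice were used.

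A reader might also infer that a uniform effect will often look selective. The documents do not support that without conditions. Section 4.2 calls 0.3 SD conservative, and by 0.5 SD the problem has all but gone. Subscales of one questionnaire rated at one visit could also be highly correlated, which puts the rate at the lower end of the range.

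One model per subscore is the natural reading of Aim 2, not its literal wording. Per-domain estimates with standard errors can be set side by side descriptively, so the subscale analyses are not useless. What is missing is a formal comparison, and section 1.2 goes beyond description when it proposes to determine which domains respond more.

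The chance of at least one significant subscale when LDX has no effect anywhere is a separate matter of multiplicity. It does not bear on selectivity between domains.

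**Conclusion.** The mismatch stands: section 1.2 poses a question about differences between domains, and no model in section 4.1, on its natural reading, tests it. This holds at any effect size.

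The numerical risk is conditional. It assumes that domains would be judged by separate tests, that all five true effects are equal, that 88 women give complete data, and that ρ lies between 0.3 and 0.9. Under those assumptions a misleading mixed pattern arises in about 21 to 56% of trials at the plan's design effect of 0.3 SD, more often at smaller effects, in about 6 to 17% at 0.4 SD, and in 2% or less at 0.5 SD.

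The subscales are supportive. The primary test on the total score and the sample size of 88 are not affected, and it would be wrong to read this point as questioning either.

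**What to change.** In Aim 2, add one joint mixed model of the five subscores:

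- Put all five on a single common scale named in advance, for example the SD of the within-woman LDX–placebo difference in change, which is the metric of section 4.2.
- Keep sequence, time and treatment. Because the plan's treatment effect is time-by-treatment, the term needed is domain-by-treatment-by-time, with its lower-order terms. A domain-by-treatment term alone would average over the pre-treatment scores and dilute the contrast. If change scores are modelled, domain-by-treatment is the right term.
- Use an unstructured within-woman covariance across domains. The change-score form is easier to fit: 5 domains × 2 periods = 10 values per woman, against 20 with pre and post scores.
- Claim differential responsiveness only if the joint 4-df test is significant at 5%. Report all five standardised LDX–placebo differences with confidence intervals either way.

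The cost is some analysis-plan wording and one extra model on data already collected. The drawback is limited power for modest differences between domains (about 30 to 66% for 0.5 against 0.3 SD at correlations of 0.3 to 0.7). The plan should therefore also state that a non-significant joint test does not show equal response.

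If the sponsor does not want a formal comparison, the alternative is to label domain comparisons as descriptive and remove the claim about greater responsiveness from section 1.2.

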1.3 Secondary Outcome Variable(s)

LDX effects on objective report of executive function difficulties. Proton magnetic resonance spectroscopy (1H-MRS) and functional magnetic resonance imaging (fMRI) will be utilized to assess the relative importance of dorsolateral prefrontal cortex (DLPFC) glutamate (Glut) levels and blood oxygen dependent (BOLD) signals during working memory task performance and the effect of LDX on the executive system activation.

2 Study Design

2.1 General Design

To further our understanding of the mechanism of LDX treatment in women with executive function complaints after risk-reducing bilateral salpingo-oophorectomy (RRSO), participants will undergo multi-modal imaging (fMRI and 1H-MTS at 7 Tesla) pre- and post- a 6-week course of LDX (20-60mg/d) or placebo followed by an approximate 2-week washout before crossing over to the other condition. This study utilizes a double-blind, placebo-controlled, cross-over design. We will recruit 100 women who are between the ages of 35 and 58 years old. Subjects will be recruited from flyers posted around campus, paid advertisements, referrals from collaborators at FORCE (Facing Our Risk of Cancer Empowered), the Basser Center, and other medical settings where women who have undergone RRSO may seek treatment. Study subjects will be screened by a member of the research staff who can gauge whether the individuals are likely to meet study criteria. Potential participants who appear to meet criteria and express an interest in the study will have the option of completing the screening visit remotely or completing the visit in-office. Participants will also have the option to complete a remote version of the study.

In-Office Screening: Participants who report for an in-office screening will be presented with the full, written ICF where they will have the chance to review and sign it with the study CRC. After giving full, written informed consent, subjects will undergo screening for past and current psychiatric disorders with the Mini International Neuropsychiatric Interview (M.I.N.I) and complete several behavioral ratings and questionnaires concerning personal history. A urine sample will be collected from participants to do a urine drug screen. Subjects will then undergo a brief medical evaluation and electrocardiogram (EKG) conducted by the study PI ([name], M.D.) or key study personnel. Vital signs including blood pressure and pulse will be recorded. Women with a consistent systolic blood pressure of >145mm Hg or diastolic blood pressure >90 mm Hg after three readings at screening will not be enrolled and referred to their primary care doctors for further evaluation. Routine laboratory studies will include TSH, FSH and estrogen assays. If potential subjects have had these tests performed within the previous 6 months and can present their results, they will forgo additional blood work except that for genetics studies (4 mL)

to examine genes related to estrogen metabolism and various neurotransmitter systems involved in cognition. These tests will assess general health and confirm postmenopausal status. The study PI will be responsible for the final decisions regarding enrollment.

Remote Screening: Participants who decide to complete the screening visit remotely must have access to telecommunication applications (i.e., Skype) that would enable the research team and participants to communicate via video chat in real-time. Furthermore, participants must have access to a scanner/fax machine so that they can send documents to the study CRC during the screening visit. Subjects who meet these stipulations will be presented with the full, written informed consent form via email and will have the opportunity to review the document in its entirety with the study CRC in real-time. After providing consent, subjects are expected to scan/fax the ICF document with their signatures to the CRC before completing other study-related procedures. The CRC will sign the document, attesting that she obtained consent, and scan/fax the document back to the subjects so that they have a copy for their records. Subjects will then undergo screening for past and current psychiatric disorders with the Mini International Neuropsychiatric Interview (M.I.N.I) and complete several behavioral ratings and questionnaires concerning personal history. Subjects will have the option of completing the brief medical evaluation, electrocardiogram (EKG), and routine laboratories studies (TSH, FSH, and estrogen levels) with their physician of choice or with key study personnel before their baseline visit. If applicable, participants will not proceed to the MRI portion of the visit until they have received medical clearance from study personnel. If potential subjects have had the blood work performed within the previous 6 months and can present their results, they will forgo additional blood work except that for genetics studies (4 mL). The study PI will be responsible for the final decisions regarding enrollment.

Participants will also review a supplemental informed consent form with a study physician, pertaining to the purpose, procedures and risks/benefits of using both of the study medications. This form will be reviewed and signed in anticipation of the participant's first dose of study medication.

Participants either unable to travel or unable to complete an MRI will be offered a remote non-imaging alternative which removes the MRI and blood draws from the required study procedures.

Baseline MRI Scan (Visit 2): Upon completion of the screening visit, subjects will be scheduled to undergo their baseline ¹H-MRS and fMRI scan session, which will take approximately 75 minutes. Subjects will be instructed to present to the Penn Center for Women's Behavioral Wellness approximately 2.5 hours before their scheduled scan to complete behavioral assessments regarding their mood and emotions and to complete out-of-scanner cognitive testing. Subjects will then be escorted to the Center for Magnetic Resonance and Optical Imaging (CMROI) by the study CRC where they will be scanned and asked to perform a series of tasks assessing their memory and attention. Subjects will then be given the study drug for the entirety of Trial A (either placebo or LDX) and instructed to begin taking the medication as directed by the study provider. If the participant needs additional study drug in order to complete the trial an additional script will be submitted to IDS for dispensation. Upon completion of the visit, the subject will be given a scale and blood pressure cuff for future remote vital sign collections. In total, the baseline scan visit will require approximately 4 hours to complete.

Additional Study Procedures for MRI eligible Subjects who Completed Screening Remotely: All subjects who completed the screening visit remotely will be reminded to bring the original version of the ICF to their Baseline MRI Scan (Visit 2) so that the original copy can be stored at PCWBW. A urine sample will be collected from all subjects to do a urine drug screen and an additional tube of blood will be collected for those who consented to genetics studies (4 mL) on the ICF before they start their scan. Subjects who indicated that they prefer research personnel to complete their required EKG and medical evaluation will be instructed to present to the Penn Center for Women's Behavioral Wellness approximately 3.5 hours before their scheduled scan to complete said procedures in addition to the assessments stipulated by Visit 2. In total, the baseline scan visit will require approximately 5 hours to complete for those that still need medical clearance.

Remote Baseline (Visit 2): Upon completion of the screening process, subjects will be scheduled for the baseline visit which will require approximately two hours. Medication will be mailed directly to the patient's home through appropriate and approved direct-to-patient services. Subjects will be prescribed study drug for the entirety of Trial A (either placebo or LDX) and instructed to begin taking the medication as directed by the study provider. If the participant needs additional study drug in order to complete the trial an additional script will be submitted to IDS for dispensation. The subject will be sent a scale (if needed) and blood pressure cuff for future remote vital sign collections. On the day of the remote baseline visit, subjects will meet remotely with a member of the study team to complete behavioral assessments regarding their mood and emotions and complete cognitive testing.

Week 2 Phone Check-In: At the end of week 2 of medication use, the CRC will check in with the participant by phone to assess for side effects. Subjects who are having more than mild side effects will be instructed to reduce their dose back to one pill per day.

Week 3 Mid-Trial Check-In: Halfway through Trial A, during their third week, subjects will be scheduled for a remote follow-up visit where they will be monitored by the CRC for potential side effects of the medication and medication compliance. If no or mild side effects are reported, subjects will be instructed to increase the study drug to three pills per day. Subjects who are having more than mild side effects will be instructed to reduce their dose back to one pill per day. The study CRC can exercise her discretion regarding medical personnel involvement at this check-in. Subjects will be instructed to complete various mood and symptoms ratings during the visit. In total, the visit will require approximately 60 minutes and will include measures of blood pressure, pulse, and weight.

Week 4 Phone Check-In: During week 4, the CRC will check in with the participant by phone to assess for side effects. Subjects who are having more than mild side effects will be instructed to reduce their dose back to 2 pills per day for the remainder of the trial.

End of Trial Scan: After the 6-week period, subjects will be scheduled to undergo their end of Trial A ¹H-MRS and fMRI scan session, which will take approximately 75 minutes. Subjects will be instructed to present to the Penn Center for Women's Behavioral Wellness approximately 2.5 hours before their scheduled scan to complete cognitive testing and behavioral assessments

regarding their mood and emotions. Subjects will then be escorted to the CMROI by the study CRC where they will be scanned and asked to perform a series of tasks assessing their memory and attention. In total, the end of Trial A scan will require approximately 4 hours to complete. The completion of this visit concludes all visits for Trial A. Upon completion of the visit and Trial A, subjects will be given the study drug for the entirety of Trial B (either placebo or LDX) and instructed to begin taking the medication after the washout period, as directed by the study provider.

Following an approximate 2-week washout period, subjects will complete their Trial B Baseline Visit, initiating the start of Trial B and medication usage. With the exception of the first baseline scan and cognitive testing, subjects will undergo the same study procedures for Trial B as they did for Trial A. Subsequent to their last scan, subjects will be required to bring their scales, blood pressure cuffs and unused capsules/empty bottles back to the study team so that they can be returned to Penn Investigational Drug Service (IDS).

The primary investigator and research staff will unblind themselves to the drug treatment that was administered in each trial upon each participant's completion or discharge from the study.

Remote End of Trial Visit: After the 6-week period, subjects will be scheduled to undergo their end of trial visit which will require approximately two hours. On the day of the remote end of trial visit, subjects will meet remotely with a member of the study team to complete behavioral assessments regarding their mood and emotions and complete cognitive testing. The completion of this visit concludes all visits for Trial A. Upon completion of the visit and Trial A, subjects will return the prescription bottle and any remaining study drug from Trial A so that they can be returned to Penn Investigational Drug Service (IDS). At this point, all subjects will be instructed to complete an approximate 2-week wash out period before continuing to Trial B.

Following an approximate 2-week washout period, subjects will be mailed their prescription for Trial B and complete their Trial B Baseline Visit remotely, initiating the start of Trial B and medication usage. Subjects will undergo the same study procedures for Trial B as they did for Trial A.

At the completion of the remote End of Trial B visit, subjects will be required to bring return the scale (if applicable), blood pressure cuffs and unused capsules/empty bottles back to the study team so that they can be returned to Penn Investigational Drug Service (IDS).

The primary investigator and research staff will unblind themselves to the drug treatment that was administered in each trial upon each participant's completion or discharge from the study.

2.2 *1H-MRS Methods*

All the single-voxel ¹H-MRS experiments to measure glutamate will be performed on a 7.0T whole body MRI scanner (Siemens Medical Systems, Erlangen, Germany) with a vendor supplied volume coil transmit/32 channel receive proton head phased array coil. BOLD signal change will be measured during performance of cognitive task and during rest.

